9 ASSESSMENT OF INVESTIGATIONAL MEDICINAL PRODUCT

Baseline demographic characteristics will consist of:

1. Age (years).
2. Gender.
3. Race.
4. Ethnicity.
5. Pompe disease history including GAA mutations and aspects of disability.
6. ECG, hematology, biochemistry, and urinalysis data from first day of avalglucosidase alfa infusion (ie, prior to first infusion in any prior avalglucosidase alfa study).

9.1 PRIMARY ENDPOINT - SAFETY

The primary endpoint of this study is safety. The following safety assessments will be collected and analyzed:

- Assessment of AEs/TEAEs, including IARs and deaths.
- Physical examination.
- Clinical laboratory evaluations, including hematology, biochemistry, and urinalysis.
- Vital signs.
- Body weight.
- 12-lead ECG.
- Immunogenicity assessments.

A β -hCG urine test will be administered to females of child bearing potential at baseline and monthly thereafter throughout the duration of the study.

9.1.1 Adverse events

Adverse events, spontaneously reported by the patient or observed by the Investigator, will be monitored throughout the study. This includes the monitoring and reporting of IARs. The safety profile will be based on incidence, severity, and cumulative nature of TEAEs.

Treatment-emergent adverse events are defined as AEs that develop or worsen during the on-treatment period. For this study, the on-treatment period will be defined as the period from the time of first dose of IMP to at least 4 weeks after the last administration of the IMP. The on-treatment period may end earlier (ie, 2 weeks after the last administration of IMP) if the patient enrolls in another study or receives commercially available ERT. For the purposes of the study, status of ongoing and new AEs will be assessed 4 weeks after the last study infusion, or for patients who discontinue early, after their last completed study visit ([Section 10.1.3.8](#)). Any new AE or serious AE (SAE) that occurs during the 4-week follow-up period and is assessed as related to the drug or study procedures will be reported/collected in the clinical database.

Definitions of AEs, SAEs, and AEs of special interest (AESIs), including reporting procedures, can be found in [Section 10.4](#) to [Section 10.6](#).

At each study visit, patients will be evaluated for new AEs and the status of existing AEs. The Investigator may elicit symptoms using an open-ended question, followed by appropriate questions that clarify the patient's verbatim description of AEs or change in concomitant medications.

Adverse events will be summarized with respect to the type, frequency, severity, seriousness, and relatedness. Pretreatment and TEAEs will be coded to a "Preferred Term (PT)" and associated primary "System Organ Class (SOC)" using the Medical Dictionary for Regulatory Activities (MedDRA). All events will be managed and reported in compliance with all applicable regulations, and included in the final clinical study report.

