Re-baseline Visit	
Physical examination (within 1 month)Urine pregnancy test (females only)Body weightVital signsECG (within 1 month)Hematology and urinalysis (within 1 month)Biochemistry	
Anti-avalglucosidase alfa antibodies and neutralizing antibodies in ADA-positive patientsAnti-alglucosidase alfa IgG antibodies (only patients who were previously treated with alglucosidase alfa)avalglucosidase alfa plasma PK samples (within 6 months)	
MRI (within 6 months)Skeletal muscle needle or open biopsy (within 6 months)^cUrine Hex4 sample collection (within 1 month)Exploratory biomarker urine sample collection (within 1 month)Exploratory biomarker plasma sample collection (within 1 month)	
6MWT (within 1 month)PFT (within 1 month)microRNA plasma sample collection (within 1 month)Serum samples for skeletal muscle RNA expression analysis (within 6 months)^c
End of Study Visit	
Physical examinationUrine pregnancy test (females only)Body weightVital signsECGHematology and urinalysisBiochemistry	
Anti-avalglucosidase alfa antibodies and neutralizing antibodies in ADA-positive patientsAnti-alglucosidase alfa IgG antibodies (only patients who were previously treated with alglucosidase alfa)avalglucosidase alfa plasma PK samples	
MRISkeletal muscle needle or open biopsy (within 6 months)^cUrine Hex4 sample collectionExploratory biomarker urine sample collectionExploratory biomarker plasma sample collection	
6MWTPFTmicroRNA plasma sample collectionSerum samples for skeletal muscle RNA expression analysis (within 6 months)^cInfusion of avalglucosidase alfa

Follow-up Visit: Adverse event and concomitant medication collection

Additional Follow-up Phase: An additional follow-up phase will begin after the patient has completed the 6-year study period, and will last until avalglucosidase alfa is approved in the patient's country, except in the UK, Germany and Denmark, where the duration of the additional follow-up phase will be up to the approval in the country or limited to a maximum of 2 years, whichever occurs first (ie, for patients in the UK, Germany and Denmark, the total study duration per patient is 8 years at the maximum including the initial 6-year period and the additional 2-year follow-up).

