1.2.3 Additional follow-up phase

Phase	Avalglucosidase alfa Follow-up Period							30-Day Follow-up Visit ^a
Timing ^b	Biweekly	Monthly	Quarterly	Every 6 Months	Yearly	Every 2 years ^c	End of Study Visit	
Visit at clinical site	<	-	-	-	-	-	>	
Concomitant medications	<	-	-	-	-	-	-	>
Study treatment administration	within a ± 7 -day window ^d							
Avalglucosidase alfa infusion	X						X	
Vital signs	X						X	
Safety ^e	within a ± 14 -day window ^d							
Physical examination				X			X	
Urine pregnancy test ^f		X					X	
Body weight			X				X	
ECG				X			X	
Hematology, urinalysis ^g				X			X	
Biochemistry ^g				X			X	
Anti-avalglucosidase alfa antibodies and neutralizing antibodies in ADA-positive patients ^h				X			X	
Adverse event collection	<	-	-	-	-	-	-	>

Phase	Avalglucosidase alfa Follow-up Period							30-Day Follow-up Visit ^a
Timing ^b	Biweekly	Monthly	Quarterly	Every 6 Months	Yearly	Every 2 years ^c	End of Study Visit	
Pharmacodynamics ^e	within a ±14-day window ^d							
MRI						X	X	
Skeletal muscle biopsy ⁱ							X	
Urine Hex4 samples ^g							X	
Exploratory biomarker plasma samples ^g					X		X	
Exploratory biomarker urine samples ^g					X		X	
Efficacy ^e	within a ±14-day window ^d							
6MWT				X			X	
PFT				X			X	
Pharmacogenetics ^e	within a ±14-day window ^d							
Plasma samples for circulating microRNA analyses ^g					X		X	

a The on-treatment period may end earlier (ie, 2 weeks after the last administration of IMP) if the patient enrolls in another study or receives commercially available ERT. In this case the follow-up period may be reduced from 4 to 2 weeks.

b In case of temporary treatment discontinuation visit and assessment schedules will be adapted to the absence of infusion of alvalglucosidase alfa as outlined in protocol [Section 10.1.3.8](#).

c If the patient discontinues from the study early then they should undergo the EOS and 30-Day follow-up visits.

d Patients should adhere to original target infusion and visit schedule based on first infusion in LTS13769.

e See [Section 10.1](#) for specific details on the timing of each assessment relative to alvalglucosidase alfa infusion during the treatment period.

f Females only.

g Fasted blood, urine, or plasma sample.

h Additional samples may be taken for circulating immune complex detection, IgE, serum tryptase, and complement activation, following moderate, severe, or recurrent mild IARs suggestive of hypersensitivity reactions (see [Section 8.8.2](#) or details).

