4.2.2 Specific parameters rationale

4.2.2.1 Safety

Safety parameters include adverse event (AE) collection, physical examination, urine pregnancy test for women of childbearing potential, body weight, vital signs, hematology, biochemistry, urinalysis, and ECG.

Patients will receive an IV infusion of avalglucosidase alfa every other week (qow). Prior to each infusion, the patient should be assessed by the Investigator or appropriate designee to determine if the patient is free of acute illness and is clinically stable to receive the infusion. Detailed infusion administration procedures can be found in the pharmacy manual.

The follow-up observation period for the end-of-study visit and for treatment-emergent adverse events (TEAE) is anticipated to be approximately 4 weeks after the last administration of avalglucosidase alfa considering the long tissue half-life of ERTs used to treat lysosomal storage diseases.

An immune reaction against an exogenously administered recombinant protein plays a critical role in the safety of the compound. Therefore, safety assessments will include blood samples for anti-avalglucosidase alfa antibodies, neutralizing antibody formation in anti-drug antibody (ADA) seropositive patients, and anti-alglucosidase alfa immunoglobulin G (IgG) antibodies (only patients who were previously treated with alglucosidase alfa).

Additional exploratory safety assessments will be conducted when clinically indicated. In the event that a patient experiences a moderate, severe, or recurrent mild infusion-associated reactions (IARs) suggestive of hypersensitivity reactions, additional blood samples will be collected for the evaluation of:

- Circulating immune complex detection; and
- Immunoglobulin E (IgE), serum tryptase, and complement activation.

Additionally, skin testing may be performed, as appropriate, in patients who experience an IAR that meets the following criteria:

- Infusion-associated reaction is suggestive of IgE-mediated hypersensitivity reaction, with persistent symptoms of bronchospasm, hypotension, and/or urticaria requiring intervention OR any other signs or symptoms at the discretion of the Investigator or the Sponsor.

Skin testing may be another predictor of IgE-mediated reaction and may be suggested for confirmation of the IgE results.

4.2.2.2 *Pharmacodynamic and exploratory biomarkers assessments*

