10 STUDY PROCEDURES

[Section 1.2](#) summarizes the schedule of study events for all patients enrolled into this study. Specific details on the timing of study assessments are provided below. The individual evaluations are described in [Section 9](#).

Medical/surgical history, and Pompe disease history, including GAA gene mutations, will be imported from the patient's prior avalglucosidase alfa study file in the database when possible.

Adverse event and concomitant medication collection will be performed at every visit throughout the study.

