10.1.3.8 Follow-up

- The Investigator should take all appropriate measures to ensure the safety of the patients, notably he/she should follow-up the outcome of any AEs (eg, clinical signs, laboratory values or other) until the return to normal or consolidation of the patient's condition.
- All AEs documented at a previous visit/contact that are designated as ongoing will be reviewed by the Investigator at subsequent visits/contacts.
- In case of any SAE, the patient must be followed up until clinical recovery is complete and laboratory results have returned to normal, or until outcome has been stabilized. This may imply that follow-up may continue after the patient has left the clinical trial and that additional investigations may be requested by the monitoring team. The Investigator will ensure that follow-up includes further investigations consistent with appropriate medical management and patient consent to elucidate the nature and/or causality of the AE.
- In case of any SAE or non-serious AE brought to the attention of the Investigator at any time after cessation of the IMP and considered by him/her to be caused by the IMP with a reasonable possibility, this should be reported to the monitoring team.

- The Investigator will provide follow-up information for any SAE to the Sponsor as soon as it is available. The Sponsor or regulatory authorities may request additional information regarding an SAE.
- For this study, the on-treatment period will be defined as the period from the time of first dose of IMP to at least 4 weeks after the last administration of the IMP. The on-treatment period may end earlier (ie, 2 weeks after the last administration of IMP) if the patient enrolls in another study or receives commercially available ERT. In this case the follow-up period may be reduced from 4 to 2 weeks. For the purposes of the study, status of ongoing and new AEs will be assessed 4 weeks after the last infusion, or for patients who discontinue early, after their last completed study visit. Any new AE or SAE that occurs during the 4-week follow-up period and is assessed as related to the drug or study procedures will be reported/collected in the clinical database.

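### Protocol 9.1.1 and 10.1.3.8 attach a relatedness condition to collecting new AEs in the 4-week follow-up; read as a filter, it conflicts with the TEAE definition, 10.4.2 and the SAP tables

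*Protocol*

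**What the plan says.** Protocol 9.1.1 sets the analysis concept first: "Treatment-emergent adverse events are defined as AEs that develop or worsen during the on-treatment period". That period runs from the first dose to at least 4 weeks after the last, and may end at 2 weeks if the patient enters another study or moves to marketed enzyme replacement. No causality condition appears. Protocol 4.2.2.1 gives the same length: "The follow-up observation period for the end-of-study visit and for treatment-emergent adverse events (TEAE) is anticipated to be approximately 4 weeks".

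The collection rule comes later in the same paragraph of 9.1.1. It concerns new events, serious or not, and the operative words are: "during the 4-week follow-up period and is assessed as related to the drug or study procedures will be reported/collected in the clinical database". Protocol 10.1.3.8 repeats it, beginning "Any new AE or SAE that occurs during the 4-week follow-up period and is assessed as related to the drug or study procedures". Section 9.1.1 then points elsewhere for procedure: "Definitions of AEs, SAEs, and AEs of special interest (AESIs), including reporting procedures, can be found in" Sections 10.4 to 10.6.

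Other places set collection without a causality condition:

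- Protocol 1.1: "Follow-up Visit: Adverse event and concomitant medication collection". In flow chart 1.2.3 the AE row extends to the 30-day follow-up visit.
- Protocol 10: "Adverse event and concomitant medication collection will be performed at every visit throughout the study".
- Protocol 10.4.2: all AEs are recorded, related or not, from consent until the patient's end of study.
- Protocol 10.4.3: any SAE is entered in the eCRF within 24 hours. Only SAEs learned of after the patient's end of study are limited to those thought to be caused by the product.
- SAP 2.1.4 and 2.1.4.1: the TEAE period includes the 28 days after the last dose (or less if protocol follow-up ends sooner), and AEs are recorded until participation ends.
- SAP 2.4.5.1: TEAEs and serious TEAEs are tabulated both irrespective of relationship and for related events.

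**The concern.** Safety is the primary endpoint of an open-label, uncontrolled study. The SAP counts the weeks after the last dose as treatment-emergent time, yet one protocol sentence, stated twice, can be taken to mean that new events in those weeks enter the database only when judged related. Sites could then work to different rules. Where the sentence is used as a filter, tables meant to show all TEAEs would lack unrelated events from the end of follow-up. What is missing would depend on an unblinded causality opinion, and related events would look like a larger fraction of the total than they are.

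The cut-off is also unclear. Protocol 11.5.3 grades causality in four levels, including unlikely and possibly related, and the collection sentence does not say which of them count as related.

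**Working it through.** There is no stated figure to reproduce. The check compares the texts and then sizes the window.

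**Side by side**

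| Source | Covers the weeks after the last dose? | Causality condition? |
|---|---|---|
| Protocol 9.1.1, TEAE definition | Yes, at least 4 weeks | No |
| Protocol 9.1.1 and 10.1.3.8, collection sentence | Yes | Yes, but no word such as *only* |
| Protocol 9.1.1 and 10.1.3.8, status check of ongoing and new AEs | Yes, at 4 weeks | No |
| Protocol 1.1 and 1.2.3, follow-up visit | Yes | No |
| Protocol 10.4.2, all AEs | Yes, if the patient's study ends at the follow-up visit | No |
| Protocol 10.4.3, SAEs | Same proviso | No, until the patient's end of study |
| SAP 2.1.4, 2.1.4.1, 2.4.5.1 | Yes | No |

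Only the collection sentence carries a condition. Flow charts 1.2.1 and 1.2.2 have no follow-up column and refer to 1.2.3, so they add nothing here.

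The proviso matters because 10.4.2 does not define the end of study for a patient. Protocol 6.2.2 defines it for the whole trial. SAP 2.1.4 takes the last follow-up visit, but cites a protocol Section 10.1.2.9 that the current protocol does not contain.

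**What a filter would remove**

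- Unrelated non-serious TEAEs starting in the window: omitted.
- Unrelated SAEs and fatal events: still required by 10.4.3, unless the site disregards it or treats the study as over before the follow-up visit.
- Deaths counted by study period (SAP 2.4.5.2): no causality condition, so not directly affected.
- Patients who stop treatment but remain in the study are followed further (Protocol 10.3.4 and 10.4.2), so the exposure is mainly at study exit.

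**Size of the window**

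Inputs: *d* is the study day of the last infusion counted from the first TDR12857 dose, using SAP Appendix B target days. *w* is 28 days, or 14 where Protocol 1.2.3 footnote a applies ("In this case the follow-up period may be reduced from 4 to 2 weeks"). Share of the TEAE period = *w* / (*d* + *w*).

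| Last infusion | *d* | *w* = 28 | *w* = 14 |
|---|---|---|---|
| LTS Month 6 | 365 | 28/393 = 7.1% | 14/379 = 3.7% |
| LTS Month 12 | 547 | 28/575 = 4.9% | 14/561 = 2.5% |
| LTS Month 36 | 1277 | 28/1305 = 2.1% | 14/1291 = 1.1% |
| LTS Month 72 | 2372 | 28/2400 = 1.2% | 14/2386 = 0.6% |

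The extreme case, a last infusion on LTS Day 1 (*d* = 183), gives 28/211 = 13.3%, or 14/197 = 7.1%. The documents do not say whether so early an exit occurs. They also give no AE rate, so these shares of time cannot be turned into a number of events.

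**The case against.** The best defence is that the sentence sets a floor. It does not exclude unrelated events, and it has work to do as a floor: an earlier bullet in 10.1.3.8 sends product-related events arising after treatment stops to the monitoring team, while this sentence puts related events from the 4 weeks into the clinical database and extends to study procedures. On that reading nothing conflicts. Section 9.1.1 sends sites to 10.4 for procedure, 10.4.2 already requires all AEs, and the flow charts and SAP agree. Those passages suggest that full collection was intended.

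Much of this stands. A reader might infer that the sentence can only be a filter; the wording does not support that. A reader might also infer that unrelated SAEs and deaths near exit would drop out of the tables. Section 10.4.3 requires any SAE to be entered and narrows to product-caused events only after the patient's end of study, so that loss needs a second departure from the protocol, or an early reading of when the study ends.

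What does not stand is that 10.4.2 settles the matter. It runs to a per-patient end of study that it leaves undefined, and a floor for related events adds little to a rule that already covers all events. A careful site could apply either reading.

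It is also fair that the analyses are descriptive, that patients who leave for marketed enzyme replacement may have the shorter window, and that a protocol amendment needs ethics approval (Protocol 15). These points limit the weight of the finding without removing it.

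**Conclusion.** The ambiguity is real and minor. Read as a filter, the sentence contradicts the protocol's own TEAE definition, its follow-up visit, 10.4.2 and the SAP. Read as a floor, it does not. The likely casualty of the filter reading is unrelated non-serious TEAEs in the final weeks; a loss of unrelated serious or fatal events is much less certain.

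The affected time is about 1% of the TEAE period for a patient treated to Month 72 and up to 7.1% for one whose last dose is at Month 6. This assumes that the last infusion falls on the SAP target day and that the TEAE period starts at the first TDR12857 dose. Only unrelated events in that window, at sites using the filter, are at risk. The documents do not show that any data were lost.

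**What to change.** In Protocol 9.1.1 and 10.1.3.8, delete the condition that the event be assessed as related to the drug or study procedures. Alternatively, replace the sentence in both places with a cross-reference to 10.4.2 and 10.4.3, stating that AEs and SAEs are recorded whatever their relationship until the patient's last follow-up visit. The second option also closes the gap left by the undefined per-patient end of study.

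This can be done at the next amendment or by erratum, a route already used for Amendment 09, with a matching line in the CRF completion instructions. If data were already collected on the related-only reading, say so as a limitation in the SAP or the study report.

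The cost is a few more AE forms at a visit that already exists, plus the amendment or erratum with whatever approvals it needs.

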9.1.2 Physical examination

Physical examination will include, at a minimum, an assessment of the patient's general appearance; skin; head, eyes, ears, nose, and throat; examinations of lymph nodes, abdomen, extremities/joints, neurological and mental status; heart and respiratory auscultation; peripheral arterial pulse; and pupil, knee, Achilles, and plantar reflexes.

9.1.3 Laboratory safety variables

The clinical laboratory data consist of blood analysis (including hematology and biochemistry) and urinalysis. Clinical laboratory values will be analyzed by a central laboratory. These values will be analyzed after conversion into standard international units, and international units will be used in all listings and tables.

Blood samples should be drawn in fasting conditions for:

- Hematology: red blood cell count, hematocrit, hemoglobin, white blood cell count with differential count (neutrophils, eosinophils, basophils, monocytes, and lymphocytes), platelets.
- Biochemistry:
 - Plasma/serum electrolytes: sodium, potassium, chloride, calcium,
 - Liver function: AST, ALT, alkaline phosphatase, gamma-glutamyl transferase, total and conjugated bilirubin,
 - Renal function: creatinine, blood urea nitrogen, uric acid,
 - Metabolic panel: glucose, albumin, total proteins, total cholesterol, triglycerides,
 - Potential muscle toxicity: creatine kinase, creatine kinase with MB fraction, lactate dehydrogenase.

Urinalysis will include urine color, appearance, specific gravity, proteins, glucose, erythrocytes, leucocytes, ketone bodies, and pH to be assessed:

- Qualitatively: A dipstick is to be performed on a freshly voided specimen for qualitative detection using a reagent strip.
- Quantitatively: A quantitative measurement for protein, erythrocytes, and leukocytes count will be required in the event that the urine sample test is positive for any of the above parameters by urine dipstick (eg, to confirm any positive dipstick parameter by a quantitative measurement).

9.1.4 Vital signs

Vital signs will include heart rate, systolic and diastolic blood pressure, respiratory rate, temperature, and oxygen saturation. Vital signs are to be assessed prior to infusion, with each infusion rate change, at the end of the infusion and at the end of the post-infusion observation period. Collection windows are ± 15 minutes.

